In group-level randomized trials design such as PIC and CPIC, the power analysis is complex because there are many factors that influence power^{176, 177}. For a simple group-level randomized trial, the power of a test such as a t-test in comparing two group means is a function of the cluster size (m), the number of clusters (J), and the intra-class correlation (ICC), the ratio of the between-cluster variability between clusters to the total variability. In our application where cluster is organization unit, we use Kish's method^{176, 177} to adjust the standard errors by the variance inflation factor (VIF) defined as $VIF=1+(m-1)\times ICC$, where ICC is the intra-class correlation at the organization unit level. For analysis of repeated measures, we use an extended formula accounting for inter-temporal correlations within individuals and within units¹⁷⁷. Based on PIC data, outcome analyses on depression care and clinic outcomes have shown that the ICC at the clinic level is either absent or around 0.01, and inter-temporal correlation coefficients within individuals and within units over a 12-month time period are greater than 0.60. PIC provider data shows that ICCs are nearly absent for provider experience and around 0.00-0.05 for knowledge. Taking a conservative approach, we assume that ICC at the unit level ranges from 0.00 to 0.02 for client data and from 0.00 to 0.05 for provider data, and that the inter-temporal correlation is 0.50. In the calculation of power for testing intervention effects from a t-test, we use degrees of freedom equal to (number of clusters – 2) when $ICC>0$, which is conservative for assessing significance, although we also explore setting degrees of freedom equal to $N-2$ (N =total sample size) for the scenario where $ICC=0$ (the optimistic scenario). We also note that regression analyses adjusting for baseline covariates and stratification variables can improve statistical power if covariates explain a substantial portion of the uncertainty.¹⁷⁷ All power analyses are conducted with power of 80% or above as adequate, assuming two-sided tests with significance level 0.05. For client data, we provide detailed power analysis for two primary study variables (appropriate depression care and probable depression).

Our initial power analyses were based on assumptions about effect sizes derived from prior studies of primary care patients, including ethnic minority patients, and that the main intervention effect would be related to increasing rates of treatments for depression. During the partnered design year, as the community leaders requested inclusion of especially vulnerable populations and services sectors for inclusion expanded, for example to faith-based agencies, senior centers, homeless-serving providers, and prisoner-reentry programs, and outcomes were added such employment, we revisited our estimates of power. First, to accommodate the interest

in employment outcomes we submitted a supplemental grant application which was funded, allowing some expansion in sample. However, even after this point, the focus on homelessness and homeless outcomes emerged in planning. This raised several scientific and operations issues, including that we might have greater attrition than planned, necessitating a larger enrolled sample, and that effect sizes might not be as large as planned, because of the greater difficulty in improving outcomes in complex populations. We therefore decided to assume that we needed approximately an increase in enrolled sample relative to our proposed sample for adequate power under more conventional conditions for fielding quality improvement interventions. These adjustments are given in the Table 3 below, including power for originally proposed sample based on prior primary care studies; power for the analysis of the same sample to address employment; and then based on revised assumptions, prior to any recruitment, to capture smaller effect sizes expected for a more clinically and socially vulnerable sample with potentially higher attrition rates. After the participatory design phase, the final study was designed to have a power of .80 with an alpha of .05 (two-sided) and ICC=.00-.02^{176, 177} to detect group difference of 10% to 11% or higher in comparing two proportions and standardized effects size of .20-.22 or higher in comparing two means. Enrolling 557-600 participants per condition (1114-1200 in total) allowed a retention rate of 65-70% at 6 month follow-up.

Table 4. Minimum detectable effect sizes for main analyses (80% power (alpha=0.05), two-sided test)*			
Note	Analytic sample size at 6 months follow-up	Effect Size†	Point Change§
Original grant	500	0.25-0.27	12.43-13.18%
With 30% expansion	650	0.22-0.24	10.92-11.78%
With further 20% expansion, final	780	0.20-0.22	9.98-10.92%

†Detectable effect size (mean difference between two groups divided by the standard deviation)¹⁷⁸. §Detectable percentage point difference for two groups.

6. CPIC 3-Year extension (PCORI award # 1845)

Background: Depression is a leading cause of morbidity with disparities in care. Depression collaborative care, a team-based approach supporting care management, patient activation and evidence-based treatments, is effective relative to usual care but often unavailable in under-resourced communities. Community Partners in Care (CPIC) randomized 95 programs in healthcare and community-based (e.g., social services, faith-based) service sectors in two communities to Resources for Services (RS) for individual program technical assistance versus

Community Engagement and Planning (CEP) for multi-sector coalition support for depression collaborative care. For depressed clients, CEP relative to RS reduced having poor mental health-related quality of life (MHRQL) and behavioral health hospitalization over 6-12 months. Longer-term outcomes are unknown.

Aims: This extension study of CPIC aims to:

1. Compare CEP and RS effects at 3-year follow-up, 2-years after intervention support, on primary (depression and MHRQL), community-prioritized outcomes of physical health-related quality of life (PHRQL) and behavioral health hospitalization, and outpatient services use (secondary);
2. Compare effects of CEP and RS at 6, 12, and 36 months for CPIC participants enrolled in healthcare or community-based service sectors;
3. Describe outcome priorities for African American and Latino depressed clients, and as perceived by providers.
4. Describe views of stakeholders planning the Los Angeles County Health Neighborhood Initiative (HNI) informed by CPIC; and national stakeholders briefed on CPIC and HNI.

We hypothesized that CEP relative to RS would improve long-term mental and physical health and reduce hospitalization nights, overall and within sector. We expected stakeholders to prioritize social factors and mental health.

Methods: Extension Study (Aims 1-3): Between 1/2014-10/2014, we approached 1004 CPIC clients initially screened as depressed from 89 programs and eligible for 3-year surveys; 600 participated (60%; RS 293, CEP 307). Aim 3: For client qualitative interviews, we approached 163 consecutive 3-year survey participants stratified by depression, race/ethnicity, gender and intervention; 104 participated (64%). For staff, we notified 289 completing 12 month surveys and used purposive follow-up stratified by community, service sector and intervention, to complete 51 interviews. Aim 4: We interviewed 49 county and community leaders planning HNI and 14 of 34 leaders attending a national briefing.

Data Sources: Self-report surveys (Aims 1 and 2) and semi-structured interviews (Aims 3 and 4).

Measures: Client outcomes are poor MHRQL ($MCS-12 \leq 40$) and depression ($PHQ-8 \geq 10$) (primary); PHRQL (12-item physical composite score (PCS-12), mental wellness, and behavioral-health hospitalization nights (community-prioritized); and use of outpatient services

(secondary). Clients and providers were asked about priorities for care and national stakeholders for responses to CPIC findings and related policy initiatives.

4-year follow-up of the 3-year sample (extension study).

The CPIC 4-year follow-up was added based on *community-stakeholder input that additional follow-up of the 3-year sample was desired to show longer-term effects on depression remission*. This follow-up built on the 3-year extension study as well as an opportunity to explore of using an existing funded cohort to recruit potential subjects into the Community and Patient Partnered Research Network (CPPRN).

Analyses plan: We will conduct 3-year end-status intent-to-treat analyses, and for 4-year follow-up of the 3-year sample, 4-year end status, with intervention status as the main independent variable, adjusted for baseline status and covariates, with response weights and multiple imputation (Aim 1); subanalyses of intervention effects within service sector at each follow-up (Aim 2); sensitivity analyses (raw data, longitudinal modeling and sector-by-intervention interactions); and thematic analyses of qualitative data (Aims 3 and 4)

7. Limitations

The proposed study is based in two under-resourced communities in Los Angeles; findings may not necessarily apply to other communities. Other limitations include the group-level randomized design, which is quasi-experimental. We rely on self-report measures and for this analysis 6-month client outcomes. This remains an ambitious study in terms of design and scope in the context of a partnered research approach.

8. Protection of Human Subjects

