Process of Care: Clients will also be asked about perceived need for treatment and how likely they would be to accept treatment or referral if it was recommended. Depressed clients will be asked at baseline and follow-up to report their use of primary care and mental health specialty services, including physician visits, prescription drugs, emergency room visits, and inpatient care over the prior six months. Following AHRQ^{13, 56, 144} and prior work we will develop an indicator of two or more months of antidepressant medication or 4 or more counseling sessions.⁴⁷ We will derive measures of use of services (e.g., primary care, mental health, emergency rooms, social service agencies, faith-based agencies). Clients who improve may not need treatment over time, so we will develop a measure of unmet need for treatment, defined as having probable depression but not receiving appropriate care versus not improved or in care. This measure combines outcomes and treatment data and thus has more power, while preserving intent to treat analyses.¹³ *(NOTE: Based on community input, services use measures were expanded to include services in a wide range of services sectors in the community relevant to depression, such as services in substance abuse agencies, telephone hotlines, self-help groups, community centers and other trusted locations).*

Outcomes of Care.

Mental and Physical Health-Related Quality of Life: Clients will complete the SF-12 at baseline and follow-up. Published results support the validity and responsiveness of the SF-12.¹⁴⁵ We found high reliability for telephone and mail-survey administration for the global scale for mental health-related quality of life MCS12 (0.84). The MCS12 is considered the primary outcome of interest as it integrates information on negative states such as psychological distress and on positive states such as wellness of particular interest to community members, and under the hypothesis that the community engagement intervention relative to technical assistance will

increase both depression treatment rates, thus lowering distress as well as increase social supports and/or address social determinants of mental health improving mental wellness.

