¹⁶⁷; development of opinion leaders,¹¹⁰ and stimulation of network development ¹¹⁸ and cross-organizational “communities of practice” that promote identification with common goals and sharing of knowledge,¹¹⁹ improving capacity for implementation.

(NOTE: Based on community input this hypothesis was modified to prioritize mental health-related quality of life as the primary outcome because it represents both positive and negative mental health states, and then to separately examine both poor mental health and mental wellness as secondary outcomes; and to expand the include physical activity as both a social determinant of mental and physical health and especially relevant to elderly clients; and also to include employment status, missed work days, and risk factors for homelessness as important outcomes. Further, the concept of quality of care was modified to reflect, in addition to traditional indicators of use of antidepressant medication and/or counseling for depression, use of depression-related case management and counseling services in alternative community services sectors. Services use was hypothesized to increase under the community engagement model relative to the technical assistance model)

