Overview: The primary goal in this group-level randomized trial is to estimate the difference in effects on outcomes, between intervention arms (e.g., CE condition vs. low-intensity control). To test our main hypotheses (that CEP would be more effective than RS in improving client health outcomes and addressing community priorities for housing and employment, while likely increasing services utilization), we will conduct intent-to-treat, comparative effectiveness analyses using intervention status as the independent variable. We will estimate logistic regression models for indicator variables and loglinear models for counts. Consistent with recommendations for group-level trials, (8) main models will incorporate adjustment for baseline status of dependent variables and covariates: age, sex, ≥ 3 chronic conditions, education, race/ethnicity, family poverty, 12-month alcohol abuse or illicit drug use, 12-month depressive disorder, and community. We will weight data for clients with baseline or six-month data to characteristics of eligible clients. For missing data, we will use item-level ^{155, 168} and wave-level ¹⁶⁹ imputation. Estimates and p-values are calculated using SUDAAN (<http://www.rti.org/sudaan/>) taking into account clustering within programs and weighting. We supplement findings from adjusted models with results from raw data to assess robustness. We will use two-sided tests with $p < .05$ for statistical significance.

We will also explore as an alternative approach multi-level models (also known as hierarchical models or random coefficient models) to account for the multilevel data structure with clients nested within units (agencies or relatively autonomous subdivisions thereof), and repeated measurements nested within clients.¹⁷⁰⁻¹⁷³ For this approach, we will apply two-level models for the cross-sectional data with clients nested within units; and three-level models for the longitudinal data with repeated measurements nested within clients and clients nested within units. To perform multilevel analyses, we will use special software such as the MIXED and GLIMMIX procedures in the SAS System V9, HLM6,¹⁷⁰ MLWin¹⁵⁹, Mplus¹⁷⁴ tailored for these analyses.

Two-level model for cross-sectional data analysis The statistical model for a “cross-sectional” analysis with one observation per client, for example Y =satisfaction at 6 months follow-up, is presented via two regression equations:

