For all study components (including supplement components discussed below), we convened working groups co-chaired by academic and community members to review analysis plans, data output and discuss findings.

Analyses for 6-month outcome: We conducted intent-to-treat, comparative-effectiveness analyses with intervention status as the independent variable, using logistic regression for dichotomous measures and Poisson regression models for count variables. Covariates were selected to account for known associations of sociodemographic and clinical status indicators with primary outcome measures. We adjusted for baseline status of dependent variables and covariates (age, sex, ≥ 3 chronic general medical conditions from a list of 18, education, race/ethnicity, family income < federal poverty level, 12-month alcohol abuse or use of illicit drugs at baseline, 12-month depressive disorder at baseline, and community). All analyses were conducted using SUDAAN Version 10.0 (<http://www.rti.org/sudaan/>) and accounted for clustering (clients within programs), weighting, and multiple imputations. Significance of comparisons by intervention status was based on regression coefficients. Results of logistic regression models are presented as odds ratios (OR) and Poisson models as rate ratios (RR) with 95 % confidence intervals. We illustrate results for intervention groups adjusted for covariates using standardized predictions generated from fitted regression models.¹⁴ We present Cohen's effect size index h , defined for dichotomous variables,¹⁵ where $h=0.20$ is small, $h=0.50$ is medium and $h=0.80$ is large. We supplement adjusted models with unadjusted raw data to assess

robustness. We applied a Bonferroni adjustment considering two primary outcomes (Poor mental health qualify of life $MCS-12 \leq 40$, and at least mild depression $PHQ-9 \geq 10$) and compared the proportion of results across outcomes favoring one intervention to an assumed null-hypothesis of 0.5.

Analyses for 12-month outcome: We conducted intent-to-treat analyses of repeated measures including all participants with available data at baseline, 6-, or 12-months by using SAS software version 9.2 (SAS Institute). We used a model-based approach with unweighted data. Initial explorations of 3-level, random-effects logistic models using SAS PROC GLIMMIX for binary outcomes yielded unstable estimates for program-specific random effects.^{16, 17}

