We conducted a longitudinal sensitivity analysis using all waves of data (baseline, 6-months, 12-months, 3-years) without response weights, adjusting for baseline covariates as in the primary analysis. We specified a spline model, with a linear segment between baseline and the first follow-up for initial improvement and another linear segment for the subsequent follow-ups; the two linear segments were specified to join at the first follow-up. In analyzing continuously scaled PCS-12 as the dependent variable, we used a 3-level, mixed-effects regression model by using SAS PROC MIXED. To account for the intraclass correlation due to the multilevel structure, we specified random effects at the program level and a spatial power covariance

structure at the client level to account for unequal spacing of waves. Initial explorations of 3-level, random-effects logistic models using SAS PROC GLIMMIX for binary outcomes yielded unstable estimates for program-specific random effects. We utilized a generalized estimating equation (GEE) framework with logistic regression models for binary outcomes and Poisson models for counts using SAS PROC GENMOD, specifying exchangeable correlation at the program level. From the estimated spline models, we developed a contrast involving a linear combination of coefficients to test intervention effects at each end point (baseline, 6-months, 12-months, and 3-years) and tested differences between intervention groups in change from baseline to 6 months, 12 months, and 3 years.

Exploratory analyses. The CPIC study had 2 primary outcomes: poor MHRQL (12-item mental health composite score, MCS-12 \leq 40), and depressive symptoms (PHQ-8 \geq 10 or PHQ-2 $<$ 3 for 4-year follow-up); and a community-prioritized outcome of mental wellness (a response of at least “a good bit of the time” in the previous 4 weeks to feeling calm or peaceful, having energy, or being happy), based on community input matched to the 36-item short-form health survey quality-of-life items. We developed 2 indicators: “clinical remission” (PHQ-8 $<$ 10 or PHQ-2 $<$ 3) and, with stakeholder input, “community-defined remission” (PHQ-8 $<$ 10 or PHQ-2 $<$ 3 or MCS-12 $>$ 40 or any mental wellness). We also used a count of survey periods in remission from baseline up to 3-year follow-up. Intervention status was the client’s program assignment at enrollment to CEP or RS.

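### The protocol makes MCS-12 quality of life primary and poor mental health secondary, but Appendix A4 treats MCS-12 at or below 40 as the primary and gives no linear endpoint model of the score at 6 months

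*Combined protocol and SAP*

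**What the plan says.** **Protocol.** Section 4.4 (Outcomes of Care) says "The MCS12 is considered the primary outcome of interest", on the ground that it captures both distress and wellness. The note under Depression Status names MCS-12 and PHQ-9 as the primary measures. In Section 5, the note to the Aim 2 hypotheses makes mental health-related quality of life primary for the same reason, "then to separately examine both poor mental health and mental wellness as secondary outcomes". Later in Section 5 the primary comparisons are described as quality of life and an indicator of probable depression, to be evaluated with baseline and 6-month data. The Final column of Table 5 (Section 11) gives mental health quality of life as the main outcome and lists poor mental health separately.

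**Models in Section 5.** The Overview says "We will estimate logistic regression models for indicator variables and loglinear models for counts". Two-level linear models for one-wave data are an alternative to be explored.

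**Appendix A4.** For 6 months: "We applied a Bonferroni adjustment considering two primary outcomes", defined there as MCS-12 at or below 40 and PHQ-9 at or above 10. The models are logistic and Poisson. The exploratory section says "The CPIC study had 2 primary outcomes: poor MHRQL", with the same cut. The 3-year endpoint analysis refers back to the 6-month strategy.

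**Extension.** Section 6 declares MCS-12 at or below 40 as a primary outcome of the 3-year study.

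**Power.** Section 5 states two sensitivities: "to detect group difference of 10% to 11% or higher in comparing two proportions", and a "standardized effects size of .20-.22 or higher in comparing two means".

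**The concern.** An outcome cannot be both secondary, as poor mental health is in the Section 5 note, and primary, as MCS-12 at or below 40 is in A4. The note and the Final column of Table 5 describe the design after community input, so this is not a conflict with superseded text.

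The two forms answer different questions. A cut at 40 separates poor from not poor. It does not register movement among clients above 40, whereas the protocol chose MCS-12 because it reflects positive as well as negative states. The forms also differ in sensitivity, and they attach to different stated power figures. Someone checking the primary result against the plan cannot tell which test was meant to carry it.

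**Working it through.** **1. The endpoint analyses, wave by wave (A4)**

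- 6 months: logistic and Poisson models, with an effect size defined for dichotomous variables. There is no linear model of MCS-12.
- 12 months: a repeated-measures analysis using baseline, 6-month and 12-month data, unweighted. MCS-12 as a continuous score is fitted in a three-level mixed model, so the 6-month scores are used here.
- 3 years: the endpoint analysis follows the 6-month strategy. The only continuous outcome named in the longitudinal sensitivity analysis is PCS-12.

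**2. The plan's own power figure**

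Inputs from Section 5 and Tables 4 and 5: two-sided alpha 0.05, power 80%, 780 analysed (780 / 2 = 390 per arm), ICC 0.00-0.02, 80-100 programs, VIF = 1 + (m - 1) x ICC.

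- Means, ICC 0: (1.960 + 0.842) x sqrt(2/390) = 0.2006. Stated: 0.20.
- Means, ICC 0.02: with 80 programs, m = 780/80 = 9.75 and VIF = 1 + 8.75 x 0.02 = 1.175. The detectable effect is 0.2006 x sqrt(1.175) = 0.2175, or 0.220 using t with 78 df. With 100 programs (VIF 1.136) it is 0.214. Stated: 0.22.
- Proportions near 50%: 9.97-10.02 points at ICC 0 and 10.7-11.0 points at ICC 0.02. Stated: 9.98-10.92.

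The final row of Table 4 reproduces in both columns.

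**3. The same shift tested on the score and on the cut (illustration)**

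Assumptions: a normal score, a favourable shift of d = 0.20 SD and 390 per arm. The documents give no expected share at or below 40, so the control share p1 runs from 30% to 70%.

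- Score: power = Phi(0.20 / sqrt(2/390) - 1.960) = Phi(0.833) = 79.8%. With ICC 0.02 and 80 programs it is 73.1%.
- Cut: p2 = Phi(z(p1) - 0.20). With D = p1 - p2 and P the mean of p1 and p2, power = Phi([D - 1.960 x sqrt(2P(1 - P)/390)] / sqrt([p1(1 - p1) + p2(1 - p2)]/390)).

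| p1 | p2 | Difference, points | Power, ICC 0 | Power, ICC 0.02, 80 programs |
|---|---|---|---|---|
| 30% | 23.4% | 6.6 | 54.4% | 48.0% |
| 40% | 32.5% | 7.5 | 58.5% | 51.8% |
| 50% | 42.1% | 7.9 | 60.3% | 53.5% |
| 60% | 52.1% | 7.9 | 60.1% | 53.3% |
| 70% | 62.7% | 7.3 | 57.6% | 51.0% |

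At ICC 0, 80% power on the cut needs a shift of about 0.25-0.27 SD instead of 0.20, or about 620-714 analysed per arm instead of 390.

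**4. Against the plan's other target**

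For 45% versus 55%, 390 per arm and ICC 0, power is 79.9%. A binary primary therefore meets the stated 10-point target.

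**The case against.** - **The protocol never calls the primary continuous.** True. Sections 4.4 and 5 name an instrument. PHQ-9 is named as primary in the same way, yet examined mainly at a cut of 10, and the main models in Section 5 are already logistic and loglinear. Nor does the note give a cut-point for poor mental health. That the score was meant is an inference. It is a strong one: the stated reason is coverage of positive states, poor mental health is listed separately, only depression is called an indicator in Section 5, and Sections 4.4 and 5 give MCS-12 no threshold.
- **A reader might infer that the declared primary is never analysed at 6 months or 3 years.** The documents do not support that. The 12-month mixed model includes the 6-month scores, Section 5 keeps a two-level linear model as an option, and the extension declares the cut as its own primary. What stands is that A4 has no linear endpoint model of MCS-12 at either wave.
- **A reader might infer that the stated power is wrong or has been lost.** It has not. Section 5 gives a separate target for proportions, which reproduces, and its detailed power work names two variables that are both binary indicators. MCS-12 in either form is not one of them. The illustration also leaves out covariate adjustment.
- **A reader might suspect that the cut was picked after seeing data.** It first appears in Section 6, after a summary of 6-12 month findings, and again in A4, written in the past tense. That shows only that this document contains no prospective statement of the threshold.
- **Replacing the primary test now would change it after results are known.** This stands, and it governs the fix.

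**Conclusion.** The inconsistency is real. Sections 4.4, 5 and 11 point to MCS-12 quality of life as primary with poor mental health apart from it; A4 makes the cut at 40 the study's primary. The missing 6-month endpoint model of the score matters most, because Section 5 assigns the primary mental health comparison to that wave. At 3 years the gap is lesser, since declaration and analysis agree within the extension.

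The sensitivity stated for means does not describe the binary test; the 10-11 point difference does. The drop from about 80% to 54-60% (73% to 48-54% at ICC 0.02 with 80 programs) shows what choosing the cut costs if the effect is a uniform 0.20 SD shift in a normal score. It depends on that shape and on the assumed share at or below 40, and it is not an error in Table 4.

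**What to change.** 1. State one form of the MCS-12 primary, in the same words, in Sections 4.4, 5 and 11 and in A4.
2. Add to A4 a linear endpoint model of MCS-12 at 6 months, and as a supporting analysis at 3 years, with the same baseline value, covariates, weights and program clustering as the existing endpoint models.
3. If the score is the primary, as Sections 4.4 and 5 indicate, report MCS-12 at or below 40 as the secondary outcome and cite the 0.20-0.22 SD sensitivity.
4. If the cut is kept, correct the Section 5 note and the Final column of Table 5, state when and why 40 was chosen, report the score model alongside, and tie the power statement to the 10-11 point difference.
5. Because A4 reports completed analyses, label any change in the form of the primary as made after results were known, and keep the existing binary result visible.

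The cost is wording in four places and one regression per wave on data already held. The score gives a less direct headline than a proportion, which the retained binary result covers.

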Assumptions of normality will also be evaluated. For example, we will explore various transformations (e.g., log and square root) for life event variables due to the often skewed distribution of event counts. Smearing estimates will be used, if necessary, for retransformation, applying separate factors for each intervention group to ensure consistent estimates.^{161, 162} In general, we leave open the possibility of transforming variables with non-normal distributions. In certain cases, the outcome of interest will have a very skewed distribution, either because there will be many zeros (e.g. sick days) and/or because the distribution of observed values has a very long tail (e.g. services utilization). In such cases, we will draw upon statistical models developed for handling these type of data, in particular a two-part model to separately handle zero values and a skewed distribution among non-zeros¹⁶¹ Tobit-type sample selection models¹⁶³; split-sample techniques to distinguish between different functional forms and to avoid overfitting¹⁶¹; and dynamic models, such as episodes of care analytic models, duration analysis, and count models.^{164, 165}

Multiple Comparisons: We will address multiple comparisons by comparing the proportion of results favoring one intervention to an assumed null-hypothesis value of 0.5. We will consider but will not rely solely on Bonferroni adjustments and related methods that incorporate bounds on the probability of a single false finding of significance. We will also consider the false discovery rate (FDR)¹⁶⁶, a framework that offers more sensitive tests of significance when large numbers of tests are carried out by comparing observed significance findings with expected order statistics from a uniform distribution.

Hypotheses and Analysis Plans for Aim 2: *To examine the effects on client access to care, quality of care, and depression-related outcomes.*

Hypotheses: We hypothesize that the community-engagement approach will lead to greater improvement over 6-12months in client's access to care, quality of care, and health outcomes than the technical assistance condition. In underserved communities, greater participation in planning, which community engagement instills, is anticipated to improve uptake of health interventions.³⁴ Further, the community-engagement intervention utilizes many principles of social-science theory that support behavior change such as practice and skill development^{104, 124,}

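### The 80% power is stated at two-sided 0.05, but Appendix A4 applies Bonferroni over two primary outcomes; at the implied 0.025, per-outcome power before covariate adjustment is about 71–73%

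*Combined protocol and SAP*

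**What the plan says.** Section 5 works at 0.05 throughout.

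- **Power for 6-Month Client Outcomes Analyses**, general rule: "All power analyses are conducted with power of 80% or above as adequate, assuming two-sided tests with significance level 0.05".
- **Same subsection**, final design: "the final study was designed to have a power of .80 with an alpha of .05 (two-sided", for ICC 0.00–0.02. The detectable differences are 10% to 11% for proportions and 0.20–0.22 SD for means.
- **Table 4**, headed as 80% power at alpha 0.05 two-sided, gives 0.20–0.22 SD and 9.98–10.92% for 780 analysed at 6 months.
- **Overview**: "We will use two-sided tests with $p < .05$ for statistical significance".
- **Multiple Comparisons**: "We will consider but will not rely solely on Bonferroni adjustments". The same paragraph plans to compare the proportion of results favouring one arm with 0.5, and to consider the false discovery rate.

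Appendix A4, under the 6-month analyses, says: "We applied a Bonferroni adjustment considering two primary outcomes". It names them as MCS-12 ≤ 40 and PHQ-9 ≥ 10, and adds the comparison of the proportion of favourable results with 0.5. It prints no per-outcome alpha.

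The power subsection also says its detailed calculations concern "two primary study variables (appropriate depression care and probable depression"), which is not the A4 pair.

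**The concern.** Table 4 and the A4 paragraph cover the same thing: the main 6-month client outcomes. Section 5 sets the threshold at 0.05 and leaves Bonferroni as something to consider. A4 says Bonferroni over two outcomes was applied, and its ordinary meaning is 0.05/2 = 0.025 for each.

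A primary p value between 0.025 and 0.05 is therefore significant under the Section 5 rule and not significant under Bonferroni. The 80% power and the 10–11 point difference hold only under the first rule. This also matters for a null result, because the detectable difference tells a reader which effects the trial could have found. No part of the document gives power or a detectable effect at the stricter level.

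**Working it through.** **Inputs**

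- N = 780 analysed (Table 4), taken as 390 per arm from the equal per-condition enrolment target.
- J = 80–100 programs (Section 4; Table 5). Section 6 says the trial "randomized 95 programs in healthcare and community-based" sectors, so J = 95 is also shown.
- ICC 0.00 to 0.02; df = J − 2 if ICC > 0 and N − 2 if ICC = 0 (Section 5, power subsection).
- Base proportion: not stated; 50% assumed.

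**Formulas**

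- VIF = 1 + (780/J − 1) × ICC
- Detectable effect (SD) = (t[1 − alpha/2] + t[0.80]) × √(2 × VIF/390)
- Percentage points from a 50% base, treating the effect as Cohen's h: 50 × sin(h)

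**Step 1. Reproduce Table 4 at alpha 0.05**

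- ICC 0: (1.963 + 0.842) × √(2/390) = 0.2009 SD, or 9.98 points.
- ICC 0.02, J = 80: VIF = 1 + 8.75 × 0.02 = 1.175; (1.991 + 0.846) × √(2 × 1.175/390) = 0.2202 SD, or 10.92 points.

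This is the printed final row. The same method with J = 80 also returns the 650 row (10.92 and 11.78 points). The method and the 50% base therefore fit the plan's own table.

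**Step 2. Detectable effect for 80% power at alpha 0.025**

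| ICC | J | VIF | t[1 − alpha/2] | Effect (SD) | Points |
|---|---|---|---|---|---|
| 0 | – | 1.000 | 2.246 | 0.2211 | 10.97 |
| 0.02 | 80 | 1.175 | 2.286 | 0.2431 | 12.04 |
| 0.02 | 95 | 1.144 | 2.278 | 0.2393 | 11.85 |
| 0.02 | 100 | 1.136 | 2.276 | 0.2383 | 11.80 |

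**Step 3. Power per outcome at the stated effects**

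Noncentral t, with noncentrality = effect × √(195/VIF):

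| Effect (SD) | ICC | J | Noncentrality | Power at 0.05 | Power at 0.025 |
|---|---|---|---|---|---|
| 0.20 | 0 | – | 2.793 | 0.797 | 0.708 |
| 0.22 | 0.02 | 80 | 2.834 | 0.799 | 0.708 |
| 0.22 | 0.02 | 95 | 2.872 | 0.811 | 0.723 |
| 0.22 | 0.02 | 100 | 2.882 | 0.814 | 0.727 |

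As a check free of design detail, a normal test with exactly 80% power at 0.05 has 71.2% at 0.025.

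**Step 4. Power for at least one primary outcome**

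Bivariate normal, with the stated effect on both outcomes. Correlations are assumed.

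| Per-outcome power | Correlation 0 | 0.5 | 0.9 |
|---|---|---|---|
| 0.708 | 0.915 | 0.849 | 0.770 |
| 0.727 | 0.925 | 0.863 | 0.787 |

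**Step 5. Covariate adjustment**

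Table 4 takes no credit for covariates. Multiply the variance by (1 − R²), with R² assumed:

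- R² = 0.10 gives per-outcome power at 0.025 of 0.757 (J = 80) and 0.776 (J = 100).
- Power of 0.80 is reached at R² = 0.182 (J = 80) or 0.148 (J = 100).
- If the inter-temporal correlation of 0.50 in Section 5 is read as a baseline-to-outcome correlation for a continuous measure, R² = 0.25 and power is 0.836 (J = 80) to 0.852 (J = 100).

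**The case against.** **A4 carries out what Section 5 allowed.** Section 5 said Bonferroni would be considered alongside the proportion-of-results comparison, and A4 does both. It never prints 0.025 and never says Bonferroni replaces p < .05. This is fair: the 0.025 rule is inferred. But A4 says the adjustment was applied, and a reader cannot tell whether it decides significance. That gap is part of the defect.

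**The 71–73% is not the power of the analysis as run.** A4 adjusts for the baseline value of each outcome and nine covariates, on a weighted and imputed sample of 1,018. With R² = 0.25, power at 0.025 exceeds 80%. This also stands as a limit. The gain may be smaller for the dichotomised outcomes that A4 analyses, Section 5 makes it conditional on how much the covariates explain, and no figure is given. A true shortfall below 80% is possible but not shown.

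**Nothing requires both primary outcomes to succeed.** Power for at least one is 0.85–0.86 at a correlation of 0.5. That is so, but Table 4 gives detectable effects for a single comparison, and it is that figure which changes.

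**Section 5 records the design before recruitment.** Rewriting it would misstate history. The 0.05 figures can stay, labelled as the design basis, with the 0.025 figures beside them.

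**Conclusion.** The concern holds. Section 5 is consistent with itself and Table 4 is right at two-sided 0.05. The stated 80% and 10–11 points do not belong to the Bonferroni test that A4 reports for the same analysis.

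Per-outcome power at 0.025 is about 71–73% instead of 80%, and the detectable effect is about 10% larger: 0.22–0.24 SD (11–12 points) in place of 0.20–0.22 SD (10–11 points). This rests on 0.025 as the meaning of Bonferroni over two outcomes, 780 analysed in equal arms, ICC 0–0.02, 80–100 programs, a 50% base, and no covariate adjustment.

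It is a mismatch between a stated figure and a described test, not proof of inadequate power. The mention of appropriate depression care as a powered primary variable is outdated wording, not a power error.

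**What to change.** State one threshold for the two primary outcomes in Section 5 (Multiple Comparisons and Overview) and in Appendix A4.

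- **If Bonferroni governs:** print 0.025 per outcome. Restate the final row of Table 4 and the matching sentence in the power subsection as about 0.22–0.24 SD and 11–12 points (50% base assumed), for 80% power per outcome before covariate adjustment. The 0.05 figures may be kept as the design basis. Any credit for covariates needs its assumed R² printed.
- **If 0.05 governs:** say in A4 that Bonferroni is supplementary. Table 4 then stands.

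In either case, update the power subsection to name the pair A4 uses at 6 months, MCS-12 ≤ 40 and PHQ-9 ≥ 10, as the powered primary outcomes.

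The cost is wording only, with no added enrolment. If Bonferroni is kept, the plan must accept a stated detectable difference about one percentage point larger.
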